- assessment of the economic impact secondary to the establishment of the figure of the Case Manager and the use of the “pharmacy of service”;
- assessment of the variation in the quality perceived by patients in carrying out this innovative treatment path, compared to the traditional model.

4. Study procedures

The study, whose duration will be 12 months (November 2018 - October 2019), which does not include any cost for the Italian National Health Service and for the same patients participating, is of type:

- observational
- prospective,
- single-center,
- no profit.

The following are the main phases of the research project.

Phase 1: Patient Enrollment (November 2018)

In the first phase, with a total duration of one month, patients are enrolled, presenting the characteristics indicated below, in a number equal to as a result of the detailed calculation in paragraph 8.

Phase 2: Review, database validation and definition of Individual Assistance Plan (December 2018)

In December 2018, the database is validated and the individual assistance plans defined by the general practitioners involved.

Phase 3: Case Management e follow up (December 2018- October 2019)

In the remaining months the Case Manager follows the patients in carrying out the checks provided by the reference PDTA and the Individual Assistance Plan drawn up by the attending physician.

ECG (performed with an electro cardiograph Microtel BT and reported by the HTN Srl power station), ocular bottom (performed with Nexty non-mydriatic fundus camera and reported by Next Sight Srl) and self-analysis (glycated hemoglobin, lipid profile and microalbuminuria, performed with Farmascreen device of Biochemical Systems International Spa) will be carried out directly in the pharmacy using the above mentioned reporting equipment and platforms. For the services requested that can not be carried out at the pharmacy, the pharmacist proceeds with the prescription from the General Practitioner, the booking of the exam by means of the CUP service and the execution of a telephone reminder service that reminds the patient when 'exam. Each performance is reported to the attending physician by sending the report in electronic format.

5. Study estimated duration

The study will last 12 months, from November 2018 to October 2019.

6. Inclusion and exclusion criteria

Recruitable patients:

- age > 18 years,
- patients with type 2 diabetes mellitus;
- able to express consent to the study

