- regularly attending the trial site (Pharmacy [name] [name])

7. Case Report Form (CRF)

Electronic data collection forms are provided (Case Report Form - CRF) necessary for the collection of clinical information of the patient, together with those of an organizational and management nature.

The detail of the information to be collected is defined in the data collection forms.

For the purpose of a homogeneous data collection, for each patient belonging to the target population, a form is provided, whose structure generally foresees the following macro-areas:

- general information on the patient (ID, gender, age, etc.);
- near and remote pathological anamnesis
- vital parameters and input blood analysis

- examinations and procedures required for follow-up
- results and reports of the controls carried out during the follow up;
- perceived quality questionnaire.

8. Sample size and statistical analysis

Starting from the percentage of adherence to all the controls envisaged by the PDTA in a historical cohort described in the work carried out by the Emilia Romagna Region on the prevalent cases of 2015 (11) equal to 4%, a simple size of 20 patients is necessary to demonstrate the effectiveness of our intervention in order to increase the percentage of adhesion to 29%, with an error α of 0.05 and a statistical power (error $1-\beta$) of 95%. To avoid any dropouts or consensus withdrawals, the necessary sample was doubled to 40 patients.

The formula used to calculate the simple size is as follows:

$$N = \frac{p_0 q_0 \left\{ z_{1-\alpha/2} + z_{1-\beta} \sqrt{\frac{p_1 q_1}{p_0 q_0}} \right\}^2}{(p_1 - p_0)^2}$$
$$q_0 = 1 - p_0$$
$$q_1 = 1 - p_1$$
$$N = \frac{0.04 * 0.96 \left\{ 1.96 + 1.64 \sqrt{\frac{0.29*0.71}{0.04*0.96}} \right\}^2}{(0.29 - 0.04)^2}$$
$$N = 20$$

p_0 = proportion (incidence) of population
 p_1 = proportion (incidence) of study group
 N = sample size for study group
 α = probability of type I error (usually 0.05)
 β = probability of type II error (usually 0.2)
 z = critical Z value for a given α or β

The statistical analysis of the collected data will be developed through descriptive analysis.

The economic evaluation will be performed by comparing the costs incurred in the traditional path and the costs deriving from the application of the model under study, calculated with reference to the regional rate where appropriate.

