The assessment of the perceived quality will be carried out through a short anonymous questionnaire administered at the end of the study to all the subjects enrolled.

All categorical variables measured in this study will be expressed as an absolute number and a percentage. Continuous variables will be expressed as mean and standard deviation or median and interquartile range [IQR], depending on the normal or non-data distribution.

The differences will be analyzed by chi-square tests, t-tests for unpaired data or by Mann-Whitney U tests, depending on the nature of the variable.

Any difference with a $p < 0.05$ will be considered statistically significant.

9. Results expected by the study

The problem of the poor adherence to the controls envisaged by the PDTA diabetes is a well-highlighted phenomenon but to which it is difficult to find a solution that gives tangible results in the short and long term, as can be seen from what can be found in the literature. The main causes of non-adherence reported in the aforementioned study (11) emerged from the focus groups conducted with patients and operators are the lack of a reference figure present continuously over time, motivating and able to give answers on several fronts (eg a nurses in group medicine and / or in the homes of health) and the difficulty of reconciling the management of the disease with the rhythms of life.

The present study by overcoming these critical issues, thanks to the use of the unexpressed potential of the “pharmacy of service” (remote execution of the services provided by the PDTA) and of the pharmacist, as a case manager, alongside the basic and specialist medicine, it will improve the current quality of care for type 2 diabetic patients (+ 25% adherence to the PDTA), with a view to sustainability.

10. Ethical Considerations

To protect privacy, the patients of the group described above will be identified only by means of progressive numerical codes (ID).

The data will be treated with confidentiality and confidentiality and disclosed only in aggregate and anonymous form.

The protection of subjects will be guaranteed as recommended in the Oviedo Convention (Convention for the Protection of Human Rights and the dignity of the human being in relation to the application of biology and medicine: Convention on Human Rights and Biomedicine - 4 April

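### The perceived-quality questionnaire is given once, at study end, with no route for patients who leave earlier and no rule for forms not returned

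*Combined protocol and SAP*

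**What the plan says.** Section 3 of the combined protocol and SAP lists among the secondary endpoints the "assessment of the variation in the quality perceived by patients in carrying out this innovative treatment path, compared to the traditional model".

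Section 8 gives the only measurement of it: "The assessment of the perceived quality will be carried out through a short anonymous questionnaire administered at the end of the study to all the"; the recipients named are every enrolled patient. Section 7 names the questionnaire as one area of the electronic case report form, without a schedule and without an early-exit form.

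On losses, Section 8 says: "To avoid any dropouts or consensus withdrawals, the necessary sample was doubled to 40 patients". It gives no expected dropout rate.

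On timing, Section 5 says: "The study will last 12 months, from November 2018 to October 2019". Section 4 places enrolment in November 2018, so most of a year separates entry from the rating.

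The analysis text in Section 8 is descriptive, with standard two-group tests. It has no rule for questionnaires that are not returned. The primary adherence percentage in Section 3 is treated differently, because its denominator is all patients enrolled.

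**The concern.** The target population and the timing pull against each other. The form is meant for everyone enrolled, but it is handed out only when the study closes, and the plan itself anticipates that some patients will have gone by then. For a patient who has withdrawn consent, the two cannot both be met. For a patient who has merely stopped follow-up, they could be, but the plan does not say how.

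The stake is selection. Patients who leave a care path may think less of it than those who stay. If so, a summary of returned forms describes the more satisfied patients while being reported as the view of patients on the new path. The primary endpoint is protected by its all-enrolled denominator, since a leaver without the scheduled checks counts as not adherent. The questionnaire has no such protection.

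The gap is also hard to repair later. A rating not taken when a patient leaves may be lost, and because the form is anonymous, the analyst probably cannot tell whose forms are missing or compare leavers with stayers.

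**Working it through.** **Step 1. Reproduce the plan's sample size.** Inputs from Section 8: historical adherence p0 = 0.04, target p1 = 0.29, z = 1.96 (two-sided α of 0.05) and z = 1.64 (power 95%).

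N = p0q0 × {1.96 + 1.64 × √(p1q1/p0q0)}² / (p1 − p0)²

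- p0q0 = 0.04 × 0.96 = 0.0384 and p1q1 = 0.29 × 0.71 = 0.2059
- √(0.2059/0.0384) = 2.316
- 1.96 + 1.64 × 2.316 = 5.758, and its square is 33.15
- N = 0.0384 × 33.15 / 0.25² = 20.37

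This agrees with the stated 20, apart from rounding down. The point made here does not touch the sample size.

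**Step 2. What the doubling implies.** 20/(1 − 0.50) = 40. The enrolled number would still leave 20 patients after a loss of 50%. This is the most the margin can absorb. It is a precaution for the primary endpoint and not a forecast.

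**Step 3. Who can be rated at study end.** The documents allow three groups to be separated.

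- Patients still in follow-up: reached by the plan as written.
- Patients who stopped follow-up but kept consent: within the stated target, but no procedure for reaching them is given.
- Patients who withdrew consent: not reachable at study end.

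**Step 4. Possible size.** The documents give no dropout rate, no scale and no satisfaction figure. The following are therefore assumptions: a satisfied/not satisfied item, 90% of stayers satisfied, 50% or 70% of leavers satisfied, and no forms from leavers. With d leavers out of 40 and a share pL of leavers satisfied:

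- share among all enrolled = [(40 − d) × 0.90 + d × pL]/40
- overstatement = 0.90 − that share = (d/40) × (0.90 − pL)
- bounds with no assumption about leavers: from (40 − d) × 0.90/40 to [(40 − d) × 0.90 + d]/40

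| Leavers d | Forms | All enrolled, pL = 50% | Overstatement | All enrolled, pL = 70% | Overstatement | Bounds |
|---|---|---|---|---|---|---|
| 4 | 36 | 86% | 4 points | 88% | 2 points | 81–91% |
| 8 | 32 | 82% | 8 points | 86% | 4 points | 72–92% |
| 12 | 28 | 78% | 12 points | 84% | 6 points | 63–93% |
| 20 | 20 | 70% | 20 points | 80% | 10 points | 45–95% |

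If leavers rate like stayers (pL = 90%), the overstatement is zero in every row.

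**Step 5. Compare with sampling error.** At d = 8 the standard error of an observed 90% is √(0.90 × 0.10/32) = 0.053. An overstatement of 8 points is 0.08/0.053 = 1.5 standard errors, and one of 4 points is 0.04/0.053 = 0.75.

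**The case against.** The strongest reply is that the plan already names all enrolled patients as recipients. Eligibility in Section 6 requires regular attendance at the pharmacy, so a patient who stops the follow-up may still come in and can be handed a form. That stands. A reader might infer that leavers cannot be scored at all, but the documents support this only for withdrawn consent.

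A reader might also infer from the doubling that up to half the patients will be lost and that the result will mainly describe those who stayed. The documents do not support that. No dropout rate is given, and the doubling is a safety margin attached to the primary-endpoint calculation. The 20-leaver row above is an extreme.

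The direction of bias is not established either. The documents do not say why patients would leave, and moving away or illness would be unrelated to satisfaction. The causes of non-adherence cited in Section 9 concern existing care, not dislike of the pharmacist-led path. With 70% of leavers satisfied and 8 lost, the bias is smaller than one standard error.

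An exit form has limits of its own. Someone who silently stops attending has no clear moment of leaving. In one pharmacy with few leavers, a left-early mark could also identify the respondent to the staff being rated.

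Finally, Section 3 promises a comparison with the traditional model, and a single end-of-study form gives no baseline or comparator unless the form itself asks for one. This is a separate question, which the change proposed here does not solve.

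These replies narrow the point. The plan still has no route to leavers and no rule for unreturned forms.

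**Conclusion.** The point holds in a limited form. The only perceived-quality measurement comes at the end of a 12-month study in which the plan anticipates losses. Patients who have withdrawn consent by then will be missed, and for other leavers nothing is specified.

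If leavers rate the path lower than stayers, the reported quality favours the new model. That is a plausible condition and not a finding. The size cannot be derived from the documents. The 4 to 8 points at 8 of 40 lost rests on assumed satisfaction of 90% among stayers and 50% to 70% among leavers, with no forms from leavers.

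The endpoint is secondary, and neither the primary analysis nor the sample size is affected. This is a cheap improvement to data collection that is best made before patients start to leave.

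**What to change.** Replace the questionnaire sentence in Section 8 with wording such as: *The same voluntary questionnaire is offered to every enrolled patient at the end of the study or, for a patient who announces leaving earlier, at that time. It is returned anonymously, for example in a sealed envelope, and carries a mark for completed or left early.*

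Add to the analysis text:

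- Report the number of forms returned out of all enrolled, separately for completers and early leavers where numbers allow this without identifying anyone.
- If leavers' forms are not obtained, limit the perceived-quality conclusion to respondents or completers.
- For yes/no items only, show the range obtained by counting all missing forms as unfavourable and then all as favourable.

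The cost is one changed sentence, a short reporting rule and one mark on an existing form, with no extra visit, staff or patients. There are downsides. Leavers rate a shorter experience, some will decline, and patients who silently stop attending may still be missed. When few leave, the left-early mark could identify a respondent, so envelopes should be opened together after the study closes and the mark reported only in aggregate.

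### The perceived-quality endpoint is a change against the traditional model, but the plan describes only one anonymous rating at study end and no rating of the traditional path

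*Combined protocol and SAP*

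**What the plan says.** Section 3 (Secondary Endpoints) sets a comparative objective: "assessment of the variation in the quality perceived by patients in carrying out this innovative treatment path, compared to the traditional model".

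Section 8 gives the measurement: a "short anonymous questionnaire administered at the end of the study to all the subjects enrolled".

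Section 7 names a "perceived quality questionnaire" among the areas of the form provided for each patient, the same form that carries the patient's ID. It gives no time point, items or comparator for the questionnaire, and it defers content: "The detail of the information to be collected is defined in the data collection forms". Those forms are not part of the document. The only intake measurements that section 7 names are "vital parameters and input blood analysis".

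For testing differences, section 8 offers chi-square tests and "t-tests for unpaired data or by Mann-Whitney U tests". No paired method is listed.

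**The concern.** A change needs two values: one for the new path and one for the traditional path. The plan describes how the first is obtained and is silent on the second. A mean score or a percentage satisfied at study end, from patients who all had the new service, cannot show whether perceived quality rose, fell or stayed the same.

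At stake is one stated secondary objective. The risk is that a favourable score at study end is reported as an improvement over usual care. If the form does ask patients to compare the two paths, the answer depends on their memory of care before the study and is given after months of using the service being rated. Recall bias and courtesy bias could then both push it in favour of the service.

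Anonymity is a lesser point. It would prevent linking a patient's two answers if a baseline were added, but it would not prevent an unpaired comparison. It also sits uneasily with section 7, where the questionnaire belongs to a form that carries the patient's ID.

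**Working it through.** **1. Search for a second value.** The places where a traditional-model value for perceived quality could come from are:

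| Possible source | What the document gives |
|---|---|
| Rating at enrolment | None described; section 7 names vital signs and blood tests at intake |
| Concurrent usual-care group | None; one centre, and all enrolled patients are followed by the case manager (sections 3 and 4) |
| Historical value | The historical cohort is named for PDTA adherence only (sections 3 and 8) |
| Comparative items in the questionnaire | Not described; items are left to forms outside the document (section 7) |

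By contrast, section 8 does name the comparator for the economic endpoint (the costs of the traditional path). The sentence on perceived quality that follows names none. The count is one occasion, one group and one path, so no difference can be computed from the measurements described.

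**2. Length of recall if comparative items exist.** Section 4 runs case management from December 2018 to October 2019. That is 11 calendar months, so a rating of the earlier path at study end would look back about 11 months.

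**3. The plan's own figure.** No figure is stated for perceived quality. The only design figure is the sample size for adherence (section 8). With p0 = 0.04 and p1 = 0.29:

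N = 0.0384 × {1.96 + 1.64 × √(0.2059/0.0384)}² / 0.25² = 20.4

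This agrees with the stated 20, which the plan doubles to 40. It does not bear on this point, except that 20 to 40 is a natural range for the number of patients with two ratings.

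**4. Illustration: what a baseline would buy, and what anonymity would cost.** The document gives no scale, standard deviation (SD), effect or correlation for the questionnaire. The following are assumptions: a roughly continuous score, a true change of 0.4 SD, a within-patient correlation r of 0.3, 0.5 or 0.7, and two-sided α = 0.05.

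- Paired t-test: dz = 0.4/√(2(1−r)), which is 0.338, 0.400 and 0.516. Power comes from the noncentral t distribution with n−1 degrees of freedom and noncentrality dz√n.
- Unpaired t-test on the same before-and-after data (both questionnaires anonymous): 100,000 simulations per cell.

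| Patients with two ratings | Analysis | r = 0.3 | r = 0.5 | r = 0.7 |
|---|---|---|---|---|
| 40 | Paired | 0.55 | 0.69 | 0.89 |
| 40 | Unpaired | 0.41 | 0.39 | 0.37 |
| 20 | Paired | 0.30 | 0.40 | 0.59 |
| 20 | Unpaired | 0.19 | 0.16 | 0.12 |

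The half-width of the 95% CI for the paired change at r = 0.5 is t(0.975, n−1) × √(2(1−r)/n):
- n = 40: 2.023 × √(1/40) = 0.32 SD
- n = 20: 2.093 × √(1/20) = 0.47 SD

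So anonymity costs precision. It does not make the change impossible to estimate. The missing traditional-path rating does.

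**The case against.** The strongest reply is that the questionnaire is not in the document. Section 3 can be read as asking for a comparative judgement from patients who have experienced both paths, and one questionnaire at the end could deliver that. This stands in part. Such items are possible, and the point made here is limited to what the plan describes. But none is described, and the result would be a recalled comparison that should be labelled as one.

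A second reply is that an enrolment questionnaire also asks about past care, and that the resulting change is an uncontrolled before-and-after difference, open to response shift and courtesy bias. The lack of a control group is a fair limitation and remains after the fix. On recall the two designs differ: at enrolment patients rate the care they are currently receiving, not care from about 11 months earlier.

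Third, anonymity protects candour when regular customers rate their own pharmacy. That is a sound reason for it, and it is why a self-generated linking code is offered below as an alternative to the study ID.

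Fourth, section 8 calls the analysis descriptive and makes no power claim for this endpoint. That is true, and the power figures are illustration only. But a descriptive change also needs two values, and section 8 goes on to specify tests of differences at p < 0.05.

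**Conclusion.** The concern holds. As described, 0 of 40 patients would have a measured change in perceived quality, and the secondary objective as worded cannot be answered. The plan yields a level at study end or, if unseen items ask for it, a recalled comparison. This rests on the document alone; the content of the data collection forms is unknown. The conclusion does not depend on the assumed 0.4 SD change or on the correlations, which only show the precision a redesigned measurement might reach. The anonymity wording and the lack of a paired test are secondary. The primary endpoint and its sample size are not affected. The plan should be changed, but this is not a flaw that undermines the study as a whole.

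**What to change.** **Preferred change**
- Give the same short questionnaire twice: at enrolment in November 2018, about the traditional path and before case management starts, and at study end or withdrawal.
- Label both with the numerical study ID of section 10 or, if anonymity must stay, with a self-generated linking code.
- Add to section 8 a paired analysis of the change (paired t-test or Wilcoxon signed-rank test) with a 95% CI, and state how many patients have both ratings.
- Reconcile the word anonymous in section 8 with the per-patient form in section 7.
- Report the result as an uncontrolled before-and-after difference.

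**If no baseline can be collected**, do one of the following:
- Add items that explicitly rate both paths, and report the result as a recalled comparison.
- Restate the endpoint in section 3 as a description of perceived quality at study end.

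**Cost.** The preferred change needs one extra short form per patient at enrolment, one sentence on the paired analysis and one wording change. The downside is possibly more courtesy bias with coded answers, because the pharmacy delivering the service is being rated. The size of that bias is not known; a linking code limits it. The baseline has to be collected before case management begins, because afterwards it can only be recalled.

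### Section 8 does not exempt costs from its normality rule, so per-patient costs judged non-normal would be reported as medians, which do not give the budget effect the economic objective asks about

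*Combined protocol and SAP*

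**What the plan says.** Section 3 lists among the secondary objectives the "assessment of the economic impact secondary to the establishment of the figure of the Case Manager and the use of the “pharmacy of service".

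Section 8 gives the economic evaluation one sentence, which opens: "The economic evaluation will be performed by comparing the costs incurred in the traditional path and the costs deriving from the application of the model". The rest of that sentence adds only that regional tariffs are used where they apply. It does not say whether the comparison is of per-patient costs, means or totals, and it names no difference measure or interval.

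The general rules come later in Section 8. For summaries: "Continuous variables will be expressed as mean and standard deviation or median and interquartile range [IQR], depending on the normal or non-data distribution". For comparisons, the plan offers chi-square tests for categorical variables and a choice between the unpaired t-test and Mann-Whitney for continuous ones. Neither rule makes an exception for costs, and no other section sets a separate one.

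**The concern.** A health system pays the total, which is the mean cost per patient times the number of patients. The mean difference between two paths therefore scales up to a budget effect. The median difference does not, and a rank test returns a p-value rather than an amount of money.

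Per-patient costs built from tariffs for discrete checks take few values and are often skewed, so non-normality is plausible, though the plan offers no data on it. If the rule is then followed as written, the economic objective is answered with a quantity that can be zero while spending per patient has changed. This matters because the protocol argues partly from cost: Section 1.1 says the role need not raise costs excessively, and Section 9 presents the model as sustainable.

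**Working it through.** **Inputs from the plan (Section 8).** Full adherence is 4% in the historical cohort and 29% targeted in the study; 40 patients are to be enrolled. The plan contains no cost figure to reproduce. Its sample-size formula with these two percentages and z = 1.96 and 1.64 gives 20.37 against the stated 20, which confirms that these are the percentages the plan works with.

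**Assumed inputs.** Each fully adherent patient costs F, and every other patient costs L, with L < F and both the same in the two paths.

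**Formulas.** With a proportion p fully adherent:

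- mean cost = p x F + (1 - p) x L
- median cost = L whenever p < 0.5
- difference in means = (0.29 - 0.04) x (F - L) = 0.25 x (F - L)
- difference in medians = L - L = 0, because 4% and 29% are both below 50%

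**Results for two assumed cost pairs.**

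| F, L | Mean, traditional | Mean, study | Difference in means | Median in each path |
|---|---|---|---|---|
| 200, 80 | 0.04 x 200 + 0.96 x 80 = 84.8 | 0.29 x 200 + 0.71 x 80 = 114.8 | +30 | 80 and 80 |
| 300, 50 | 0.04 x 300 + 0.96 x 50 = 60.0 | 0.29 x 300 + 0.71 x 50 = 122.5 | +62.5 | 50 and 50 |

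**What Mann-Whitney adds.** With only two cost values, the tie-corrected test behaves like a comparison of two proportions. Take 12 of 40 study patients and 2 of 40 comparators at the higher cost (the comparator size of 40 is an assumption). The two-sided p-value is about 0.0035. In repeated simulation at 40 v 40 the test rejects in about 90% of runs. With F = 200 and L = 80 the means in that sample are 116 and 86, and both medians are 80. The report would show a significant p-value beside identical medians, and the difference of 30 would not appear.

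**Precision of the proposed estimate.** In the first example the standard error of the study mean is (200 - 80) x sqrt(0.29 x 0.71 / 40) = 8.6. The 95% half-width is about 1.96 x 8.6 = 16.9 if the traditional-path mean is a fixed figure. The interval is wide, but it is in money and can be used.

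**The case against.** **The rule may not govern costs at all.** The economic evaluation has its own sentence, which can be read as one path's cost against the other's at tariff. The case report form areas in Section 7 name no cost variable. If only tariff totals are compared, no median arises. This stands, and it makes the point conditional. But the plan does not say that totals are used, and Section 7 does collect the checks carried out, from which patient-level costs could be built.

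**Mann-Whitney may not be possible.** It needs individual costs in both groups. The plan describes one enrolled cohort and a historical comparator taken from a regional report, and no patient-level costs for the traditional path. This also stands. It removes the test but not the problem of a median for the study cohort.

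**The two-point model is artificial.** Reminders and in-pharmacy testing could raise partial completion and so move the median, and F and L need not be equal across paths. The exact zero is a product of the assumptions. A median that moved would still not be the budget effect.

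**A reader might infer that the planned test would miss a rise in cost.** The documents do not support this. In the example built on the plan's own percentages the test is usually significant. A test that stays near its 5% error rate can be produced by assuming lognormal costs with equal medians and different spreads (5.0% to 5.8% rejection at an assumed 40 v 40, with mean cost 22% to 81% higher), but nothing in the plan points to that distribution.

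**A reader might also infer that costs are certain to be reported as medians.** That too goes beyond the text: the rule gives means if costs are judged normal, and the plan names no normality test.

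**Conclusion.** The concern holds in a conditional form. If per-patient costs are analysed and judged non-normal, Section 8 selects the median, which is the wrong summary for an economic impact. Under the two-point model with common assumed costs, the plan's 4% and 29% give a median difference of 0 against a mean difference of 0.25 x (F - L). The size in money depends wholly on F and L, which the plan does not give.

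The defect lies in the quantity reported. It is not established that a test would show no difference, or that costs will fall under the rule. The endpoint is secondary, and the primary endpoint and its sample size are unaffected. The change is worth making because it is cheap and settles how costs will be summarised before data are seen.

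**What to change.** Add to Section 8, after the sentence on the economic evaluation: *Costs will be reported as the arithmetic mean cost per enrolled patient, and the total, in each path, whatever their distribution, with the difference in means and a bootstrap 95% confidence interval. Medians are supplementary description only. Where the traditional path has only a tariff-based mean, the study mean and its bootstrap interval will be compared with that figure.*

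Replacing Mann-Whitney by a t-test would not be enough, because the reader needs the estimated difference and its uncertainty rather than another p-value.

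The cost is this short addition and a short bootstrap, with no new data. The downside is that the interval may be wide with 40 patients; the report should show that width.
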